8.6.4. Stopping Rule for Potassium

In the event of confirmed potassium of ≥ 6.0 mmol/L or ≥ 5.5 mmol/L at any time during the study *with* new ECG changes consistent with hyperkalemia, dosing of a subject with Study Drug will be stopped permanently. The subject should stop any medications (e.g., ACE/ARB, K+ sparing diuretics, eplerenone) or high K+ diet/supplements affecting potassium levels. Measure potassium frequently until documented to be < 5.5 mmol/L. If there are ECG changes consistent with hyperkalemia or muscle weakness the subject should be admitted to the hospital. The Investigator may consider obtaining a nephrology consultation with consideration for dialysis to treat hyperkalemia. Additional consultation of the Investigator with the Sponsor Medical Monitor may be considered to individualize treatment plan.

8.6.5. Stopping Rule for Blood Pressure

1. In the event of a SBP ≤ 90 mmHg with symptoms of hypotension (i.e., dizziness, light-headedness, clammy skin, fatigue, blurry vision), as measured by home BPM, at any point in the study, the patient should contact the Study Center immediately and have the SBP confirmed by the Study Center. If confirmed and the patient remains symptomatic, dosing of a subject with Study Drug will be interrupted. If patient is still symptomatic after instituting IV hydration (see Section 8.5.3 Safety Monitoring Rules for Blood Pressure), the patient should be admitted to the hospital. Timing for re-institution should be assessed depending on the reversibility of initiating factors (decreased oral intake, cold/flu, other illness). If the subject remains symptomatic Study Drug should be stopped permanently. If this occurs in the follow-up period, any other antihypertensives or other medications that could affect BP should be stopped, if feasible. The use of IV angiotensin II or vasopressors should be considered in subjects that remain symptomatic and are hemodynamically unstable. The subject will continue to be followed per protocol

in the study. Follow-up for subjects that screen fail due to blood pressure inclusion criteria (see Section 5.1) will not be necessary.

2. During the Treatment Period, should a subject experience a BP measurement > 170 mmHg (systolic) or > 110 mmHg (diastolic) a second measurement must be done within a 30-minute period. If the subject's BP is >170 mmHg (systolic) or > 110 mmHg (diastolic) within the 30-minute period, an additional BP measurement should be taken within 48 hours at the Study Center, regardless of whether the initial BP measurements were taken in clinic or at home. If the subject then experiences a BP measurement > 170 mmHg (systolic) or > 110 mmHg (diastolic) (confirmed by triplicate measurement at the Study Center), they will then be withdrawn from further blinded, randomized treatment. The subject's pre-study antihypertensive medication(s) may be added back per Investigator and Sponsor Medical Monitor judgement. The subject will continue to be followed per protocol in the study.

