6.1.4. Treatment Period

Eligible subjects will be administered Study Drug (ISIS 757456 or placebo) on a weekly basis (6 weeks) as well as an additional dose on Study Day 3 for a total of 7 doses. Review of the at-home blood pressures and the in-clinic BP should be performed prior to administering the Study Drug.

Safety and clinical laboratory evaluations as well as blood sampling for PK analysis will be performed periodically throughout the Treatment Period ([Appendix A](#), [Appendix B](#), and [Appendix C](#)). Any AEs and concomitant medications will be recorded. If antihypertensive medications are re-instated this will be captured in the concomitant medications eCRF. All safety data including AEs, at home and in-clinic BP, and concomitant medications will be reviewed by the Sponsor's Medical Monitor or designee on an ongoing basis throughout the trial.

Subjects will continue at home BP and HR monitoring during the Treatment Period as outlined in Section [6.1.1.3](#) and [Appendix A](#). Subjects who discontinue the Treatment Period early will continue in the study following the post-treatment evaluations (Section [6.1.5](#))

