8.5. Safety Monitoring Rules

Please refer also to the 'Guidance for Investigator' section of the ISIS 757456 Investigator's Brochure.

In addition to the standard monitoring of clinical safety parameters, the following guidelines are provided for the monitoring of selected parameters chosen based on preclinical and clinical observations.

Confirmation Guidance: At any time during the Study (Treatment or Post-Treatment Periods), the initial clinical laboratory results meeting the safety monitoring criteria presented below must be confirmed by performing measurements (ideally in the same laboratory that performed the initial measurement) on new specimens. All new specimen collections should take place as soon as possible (ideally within 3 days of the initial collection). For stopping rules, if the initial laboratory result is observed during the Treatment Period, the results from the retest must be available prior to administering the next dose of Study Drug (ISIS 757456 or placebo).

Re-dosing Guidance: Subjects with initial laboratory test values that reach a stopping rule must not be re-dosed until the re-test results are available. In general, subjects who do not meet the stopping rules based upon retest may continue dosing. However, the Investigator and the Sponsor Medical Monitor (or appropriately qualified designee) should confer as to whether additional close monitoring of the subject is appropriate. If any of the stopping criteria described below (refer to Section 8.6.1 to Section 8.6.5) are met, the subject will be permanently discontinued from further treatment with Study Drug (ISIS 757456 or placebo), evaluated fully as outlined below and in consultation with the Sponsor Medical Monitor or appropriately qualified designee, and will be followed-up in accordance with Section 8.8.

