8.5.3. Safety Monitoring Rules for Blood Pressure

1. In the event of a SBP \leq 100 mmHg a second measurement must be done within a 30-minute period. If the subject's SBP is \leq 100 mmHg within the 30-minute period, an additional BP measurement should be taken within 48 hours at the Study Center, regardless of whether the initial BP measurements were taken in clinic or at home. If the subject then experiences an additional SBP measurement \leq 100 mmHg (confirmed by triplicate measurement at the Study Center), or if the subject is symptomatic (i.e., dizziness, light-headedness, clammy skin, fatigue, blurry vision), the dose will be withheld. Vital signs should be confirmed, and orthostatic hypotension assessment should be performed (See Section 6.1.1.2). In addition, the subject will have home BPM 2 times per day for 1 week. Subject should orally hydrate with 1-liter fluids, including fluids with electrolyte solution (sports drink, etc.). If the subject is symptomatic the Investigator should consider admitting for observation and consider instituting intravenous (IV) hydration with 1-liter normal saline solution and reassess symptoms and orthostatic hypotension assessment. When SBP is $>$ 100 mmHg and is asymptomatic then patient should continue dosing. If the patient has orthostatic vital signs and is asymptomatic, the dose should be withheld until orthostatic hypotension is resolved. The subject will continue to be followed per protocol in the study. Follow-up for subjects that screen fail due to blood pressure inclusion criteria (see Section 5.1) will not be necessary.

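### The stopping rule for symptomatic SBP of 90 mmHg or less is written for home readings only, and Sections 8.5, 8.5.3, 8.6.5 and 8.8 do not agree on what follows

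*Combined protocol and SAP*

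**What the plan says.** Five places in the protocol bear on this point.

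- **8.6.5 item 1 (stopping rule, low BP).** The trigger is SBP of 90 mmHg or less with symptoms, "as measured by home BPM, at any point in the study, the patient should contact the Study Center immediately"; the Study Center then confirms the reading. On dosing it says: "If confirmed and the patient remains symptomatic, dosing of a subject with Study Drug will be interrupted". If symptoms continue after IV hydration, "the patient should be admitted to the hospital". The timing of re-institution is to be assessed against reversible causes. Finally: "If the subject remains symptomatic Study Drug should be stopped permanently".
- **8.5.3 item 1 (monitoring rule, low BP).** The trigger is SBP of 100 mmHg or less on repeat, with a Study Center reading within 48 hours "regardless of whether the initial BP measurements were taken in clinic or at home". A further low reading there, or symptoms, means that the dose is withheld. Admission and IV hydration are for the Investigator to consider. When SBP is above 100 mmHg "and is asymptomatic then patient should continue dosing".
- **8.6.5 item 2 (stopping rule, high BP).** It carries the same clinic-or-home clause as 8.5.3.
- **8.5 (Re-dosing Guidance).** "If any of the stopping criteria described below (refer to Section 8.6.1 to Section 8.6.5) are met, the subject will be permanently discontinued".
- **8.8 (Discontinuation of Study Drug).** It requires a permanent stop for laboratory results meeting 8.6.1 to 8.6.3 and for an adverse event that makes it necessary. It does not list 8.6.4 or 8.6.5.

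Section 6.1.4 adds: "Review of the at-home blood pressures and the in-clinic BP should be performed prior to administering the Study Drug".

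**The concern.** Clinic BP is looked at before each injection, so it is foreseeable that symptomatic low BP is detected first in the clinic. Yet the stopping rule for that event names only home readings. The two neighbouring BP rules cover both settings explicitly, which makes the omission in item 1 stand out.

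What is at stake is consistent handling of a safety event that the protocol itself singles out: hypotension is named among the safety endpoints (Section 1.2.3). Two subjects with the same SBP and the same symptoms could meet different written requirements on admission, on resuming Study Drug and on permanent stopping, depending only on where the cuff was first used. Even where 8.6.5 item 1 clearly applies, a site that reads it beside 8.5 finds two different answers on whether the stop is permanent.

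**Working it through.** No arithmetic applies: the question is the scope of a rule. The check is to follow one event, SBP of 88 mmHg with dizziness, from each starting place.

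**Step 1. Which rules are triggered?** A home reading of 88 is at or below both 100 and 90, so it meets 8.5.3 item 1 and, on the home clause, 8.6.5 item 1. A clinic reading of 88 meets 8.5.3 item 1. It does not meet 8.6.5 item 1 as written, because it was not measured by the home device.

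**Step 2. What does each path require?**

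| | First found at home (8.5.3 and 8.6.5 item 1) | First found in clinic (8.5.3 only) |
|---|---|---|
| Dose while symptomatic | Withheld under 8.5.3; interrupted under 8.6.5 after confirmation with continuing symptoms | Withheld |
| Admission | Directed if symptoms persist after IV hydration | To be considered |
| Resumption | Timing assessed against reversible causes (8.6.5) | Continues once SBP is above 100 mmHg without symptoms |
| Permanent stop | Stated if symptoms remain | Not stated |
| Other BP-lowering drugs in follow-up | To be stopped if feasible | Not stated |

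The clinic path is the home path without the 8.6.5 consequences.

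**Step 3. Does anything carry the clinic case across to 8.6.5?** The potassium monitoring rule (8.5.2) sends the reader on to the stopping rules, and the platelet monitoring rule (8.5.4) refers to 8.6.3. Section 8.5.3 item 1 has no such link. The reference runs the other way only: 8.6.5 item 1 points back to 8.5.3 for IV hydration. There are two indirect routes. Section 8.5.3 puts the subject on twice-daily home readings for a week, so an event that continues at 90 mmHg or less with symptoms can later be read at home and enter 8.6.5. Section 8.8 allows an adverse-event-based permanent stop, but by judgement and with no BP threshold.

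**Step 4. What does meeting 8.6.5 item 1 mean?** Section 8.5 says permanent discontinuation and names 8.6.5 in its range. Section 8.6.5 item 1 says interruption, possible re-institution, and a permanent stop only if symptoms remain. The stopping-rule entry in 8.8 is limited to laboratory results and ends at 8.6.3, so it does not settle the matter. This conflict affects home-first events too and is separate from the location gap.

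**The case against.** The best case for the plan is that the gap has little practical effect, and much of that case stands.

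- **The dose is held either way.** A reader might infer that a symptomatic subject at 88 mmHg in the clinic could be injected. The documents do not support that: 8.5.3 item 1 withholds the dose for symptoms at 100 mmHg or less, and 6.1.4 requires BP review before dosing.
- **The rules are not in the wrong order.** A reader might infer an inversion, because 8.6.5 waits for confirmation and continuing symptoms while 8.5.3 holds on symptoms alone. But any SBP of 90 mmHg or less also meets 8.5.3, so the hold is already in force and 8.6.5 adds to it.
- **The end results often coincide.** Under 8.5.3 dosing resumes only when symptoms have gone, so a subject who stays symptomatic is not re-dosed under either rule. With the last dose on Day 36, a long hold and a permanent stop can amount to much the same thing.
- **A natural reading narrows the gap.** The home clause tells the patient whom to call, and the operative step is Study Center confirmation with continuing symptoms. An investigator may treat a symptomatic clinic reading as that confirmation. This is reasonable, but it is not written, and sites may differ.

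Two further inferences also fail. Counting scheduled clinic readings against home readings gives a share of measurement occasions, not a risk of the event. And an effect on the Per Protocol Set, which needs at least 5 of 7 doses, is not shown: both rules hold doses, and nothing in the documents shows a case where the choice of rule moves a subject across that line.

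What the objection does not remove is the difference in written requirements in Step 2 or the conflict in Step 4.

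**Conclusion.** The point holds as an inconsistency between stated rules, of minor severity. For SBP of 90 mmHg or less with symptoms first found in the clinic, the protocol has no written directed admission, re-institution assessment or permanent stop, unless a later home reading brings the event into 8.6.5 or the adverse-event route in 8.8 is used. Separately, 8.5 and 8.6.5 item 1 disagree on whether meeting the rule is permanent, and 8.8 does not resolve it.

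The conclusion rests on reading the home clause literally; on the looser reading described above, the location gap becomes a matter of clarification, while the conflict with 8.5 remains. The documents give no hypotension rate, so the number of subjects affected cannot be estimated.

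**What to change.** Reconcile 8.5 (Re-dosing Guidance), 8.5.3 item 1, 8.6.5 item 1 and 8.8, so that the same SBP with the same symptoms leads to one stated action wherever it is first measured, and so that all four sections agree on whether that action is temporary or permanent. The clinic-or-home clause in 8.5.3 and 8.6.5 item 2 is available if the sponsor wants the rule to cover both settings. If the home restriction is intended, the protocol should say so and state what applies to a clinic-first event. Which action applies is the sponsor's clinical decision.

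The cost is a short protocol amendment and a memo to sites. The one downside is that a few clinic-detected events may be handled differently from now.

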8.7. Adjustment of Study Drug Dose or Schedule

If the safety profile warrants, and subjects have not met a stopping rule, Study Drug may be adjusted downward in consultation with the Sponsor Medical Monitor or designee.

8.8. Discontinuation of Study Drug

A subject must permanently discontinue study treatment for any of the following:

- The subject withdraws consent
- The subject experiences an AE that necessitates permanent discontinuation of Study Drug
- The subject develops laboratory test abnormalities that meet any of the stopping rules listed in Section 8.6.1 to Section 8.6.3
- The subject experiences an AE that necessitates unblinding of the Investigator to the subject's treatment assignment

The reason for discontinuation of Study Drug treatment must be recorded in the electronic Case Report Form (eCRF) and source documentation.

For subjects withdrawn for reasons other than withdrawal of consent every effort should be made to complete the early termination study procedures and observations at the time of withdrawal (see [Appendix A](#)) and ideally within 2 weeks from the last dose of Study Drug.

8.9. Withdrawal of Subjects from the Study Procedures

Subjects must be withdrawn from study procedures for any of the following:

- Withdrawal of consent
- The subject is unwilling or unable to comply with the protocol

Other reasons for withdrawal of subjects from study procedures might include:

- At the discretion of the Investigator for medical reasons
- At the discretion of the Investigator or Sponsor for noncompliance
- Significant protocol deviation

All efforts will be made to complete and report the observations as thoroughly as possible up to the date of withdrawal. All information, including the reason for withdrawal from study, must be recorded in the eCRF.

Any subject who withdraws consent to participate in the study will be removed from further treatment and study observation immediately upon the date of request. These subjects should be encouraged to complete the early termination study procedures and observations at the time of withdrawal ([Appendix A](#)) and ideally within 2 weeks from the last dose of Study Drug.

For subjects withdrawn for reasons other than withdrawal of consent every effort should be made to complete the early termination study procedures and observations at the time of withdrawal (see [Appendix A](#)).

8.10. Concomitant Therapy and Procedures

The use of concomitant therapies or procedures defined below must be recorded on the subject's eCRF. Adverse events related to administration of these therapies or procedures must also be documented on the appropriate eCRF.

8.10.1. Concomitant Therapy

A concomitant therapy is any non-protocol specified drug or substance (including over-the-counter medications, herbal medications and vitamin supplements) administered between screening and Post-Treatment Evaluation Period.

8.10.1.1. Allowed Concomitant Therapy

Any other medications deemed necessary by the Investigator are allowed except those listed in the disallowed concomitant therapy.

If the criteria in Section [8.5.3](#) (blood pressure monitoring rules) are met and the patient is in the Post-Treatment Period, antihypertensive agents may be added for BP control in consultation with the Investigator and Sponsor Monitor or designee.

8.10.1.2. Disallowed Concomitant Therapy

The following are disallowed concomitant therapies:

- Medications for the treatment of HTN (e.g., clonidine, guanfacine, guanabenz, alpha-methyldopa, hydralazine, minoxidil, diazoxide, renin inhibitors) (unless required for safety reasons to control BP in the Post-Treatment Period)
- Medications that may also cause hyperkalemia (e.g., cyclosporine or tacrolimus, pentamidine, trimethoprim-sulfamethoxazole, all heparins)

- Oral or subcutaneous anticoagulants (e.g., warfarin, rivaroxaban, apixaban, lovenox, heparin). Organic nitrate preparations (e.g., nitroglycerin, isosorbide mononitrate, isosorbide dinitrate, or pentaerythritol)
- Sildenafil, tadalafil, vardenafil

8.10.2. Concomitant Procedures

A concomitant procedure is any therapeutic intervention (e.g., surgery/biopsy, physical therapy) or diagnostic assessment (e.g., blood gas measurement, bacterial cultures) performed between screening and the end of the Post-Treatment Evaluation Period.

8.11. Treatment Compliance

Compliance with treatment dosing is to be monitored and recorded in the eCRF by Study Center staff.

9. SERIOUS AND NON-SERIOUS ADVERSE EVENT REPORTING

9.1. Sponsor Review of Safety Information

Safety information will be collected, reviewed, and evaluated by the Sponsor or designee in accordance with the applicable Ionis and/or designee SOPs throughout the conduct of the clinical trial.

9.2. Regulatory Requirements

The Sponsor is responsible for regulatory submissions and reporting to the Investigators of serious adverse events (SAEs) including suspected unexpected serious adverse reactions (SUSARs) per the International Conference on Harmonization (ICH) guidelines E2A and ICH GCP. Country-specific regulatory requirements will be followed in accordance with local country regulations and guidelines.

Institutional Review Boards (IRBs) will be notified of any SAE according to applicable regulations.

The Sponsor or designee will evaluate the available information for all reported SAEs and decide if there is a reasonable possibility that the Study Drug (ISIS 757456 or placebo) caused the AE and, therefore, meets the definition of a SUSAR.

Appropriate personnel at the Sponsor will unblind SUSARs for the purpose of regulatory reporting. The Sponsor will submit SUSARs to Regulatory Agencies in blinded or unblinded fashion according to local law. The Sponsor will submit SUSARs to Investigators in a blinded fashion.

For the purpose of regulatory reporting of SUSARs, there are no “expected” AEs in this study population. For Study Drug (ISIS 757456 or placebo) “expected” AEs, refer to the Investigator’s Brochure.

9.3. Definitions

9.3.1. Adverse Event

An adverse event (AE) can be any unfavorable and unintended sign (including an abnormal laboratory finding, for example), symptom, or disease temporally associated with the use of medicinal (investigational) product, whether or not the AE is considered related to the medicinal (investigational) product.

An AE can therefore be any of the following:

- Any unfavorable and unintended sign (including an abnormal laboratory finding), symptom, or disease temporally associated with the use of a medicinal product, whether or not considered related to the medicinal product
- Any new disease or exacerbation of an existing disease (a worsening in the character, frequency, or severity of a known condition)
- Recurrence of an intermittent medical condition (e.g., headache) not present at Baseline
- Any deterioration in a laboratory value or other clinical test (e.g., ECG, X-ray) that is associated with symptoms or leads to a change in study treatment or concomitant treatment or discontinuation from Study Drug
- Adverse events that are related to a protocol-mandated intervention, including those that occur prior to assignment of study treatment (e.g., screening invasive procedures such as biopsies)

9.3.2. Adverse Drug Reaction and Unexpected Suspected Adverse Drug Reaction

Adverse Drug Reaction (ADR)

In the *pre-approval* clinical experience with a new medicinal product or its new usages, particularly as the therapeutic dose(s) may not have been established, ADR is defined as follows:

All noxious and unintended responses to a medicinal product related to any dose should be considered adverse drug reactions.

The phrase "responses to a medicinal product" means that a causal relationship between the medicinal product and the AE has been determined by the Sponsor as at least a reasonable possibility, i.e., the relationship cannot be ruled out.

Suspected Unexpected Adverse Drug Reaction

A suspected unexpected ADR is any ADR, the nature or severity of which is not consistent with the applicable product information, e.g., Investigator's Brochure for an unapproved medicinal (investigational) product.

A suspected adverse reaction implies a lesser degree of certainty about causality than an adverse reaction.

